10.1 Confidentiality

All laboratory specimens, evaluation forms, reports, and other records will be identified in a manner designed to maintain subject confidentiality. All records will be kept in a secure storage area with limited access. Clinical information will not be released without the written permission of the subject (or the subject's legal guardian), except as necessary for monitoring and auditing by the sponsor, its designee, or the IEC.

The investigator and all employees and co-workers involved with this study may not disclose or use for any purpose other than performance of the study any data, record, or other unpublished, confidential information disclosed to those individuals for the purpose of the study. Prior written agreement from the sponsor or its designee must be obtained for the disclosure of any said confidential information to other parties.

10.2 Financial Disclosure and Obligations

Neither the sponsor nor the CRO is financially responsible for further testing or treatment of any medical condition that may be detected during the screening process. In addition, in the absence of specific arrangements, neither the sponsor nor the CRO is financially responsible for further treatment of the subject's disease.

10.3 Investigator Documentation

Prior to beginning the study, the investigator will be asked to comply with ICH E6 (current version) by providing all essential documents.

10.4 Study Conduct

The investigator agrees that the study will be conducted according to the principles of ICH E6 (current version). The investigator will conduct all aspects of this study in accordance with all national, state, and local laws or regulations. Study information from this protocol

will be posted on publicly available clinical trial registers before enrolment of participants begins.

The investigator agrees to conduct the study as outlined in this protocol in accordance with ICH E6 (current version) and all applicable guidelines and regulations.

10.5 Adverse Events and Study Report Requirements

The investigator agrees to submit reports of SAEs to the sponsor and/or IEC according to the timeline and method outlined in the protocol. In addition, the investigator agrees to submit annual reports to the study site IEC as appropriate.

10.6 Investigator's Final Report

Upon completion of the study, the investigator, where applicable, should inform the institution; the investigator/institution should provide the IEC with a summary of the study's outcome and the sponsor and regulatory authority(ies) with any reports required.

10.7 Records Retention

Essential documents should be retained until at least 2 years after the last approval of a marketing application in an ICH region and until there are no pending or contemplated marketing applications in an ICH region or at least 2 years have elapsed since the formal discontinuation of clinical development of the investigational product. These documents should be retained for a longer period, however, if required by the applicable regulatory requirements or by an agreement with the sponsor. It is the responsibility of the sponsor to inform the investigator/institution as to when these documents no longer need to be retained. No records may be transferred to another location or party without written notification to the sponsor.

10.8 Publications

After completion of the study, the data may be considered for reporting at scientific meetings or for publication in scientific journals. In these cases, the sponsor will be responsible for these activities to determine how the manuscript is written and edited, the number and order of authors, the publication to which it will be submitted, and other related issues. The sponsor has final approval authority over all such issues.

Data are the property of the sponsor and cannot be published without prior authorization from the sponsor, but data and publication thereof will not be unduly withheld.

11 Study Management

The administrative structure will include an unblinded biostatistics team (statisticians and programmers) and an external SMC.

11.1 Monitoring

11.1.1 External Data Monitoring Committee

11.1.1.1 Safety Monitoring Committee

Safety oversight will be conducted by an SMC that is an independent group of experts that monitors subject safety and advises the sponsor. The SMC members will be separate and independent of study personnel participating in this study and should not have scientific, financial, or other conflict of interest related to this study. The SMC will consist of members with appropriate expertise to contribute to the interpretation of the data from this study.

The SMC will convene prior to study initiation, if a pause is triggered, or upon the request of the medical monitor and/or sponsor. The medical monitor and sponsor are empowered to request a review by the SMC for any safety reason.

The SMC will operate under the rules of a sponsor-approved charter that will be approved at the organizational meeting of the SMC. At this time, each data element that the SMC needs to assess will be clearly defined. Procedures for SMC reviews/meetings will be defined in the charter. The SMC will review applicable data to include, but not limited to subject's clinical course or safety results (eg AEs, reactogenicity). Reports may include enrolment and demographic information, medical history, concomitant medications, physical assessments, and solicited and unsolicited AE/SAEs. Additional data may be requested by the SMC, and interim statistical reports may be generated as deemed necessary and appropriate by the sponsor. The SMC may receive data in aggregate and presented by treatment group.

The SMC will review grouped and unblinded data in the closed session only. As an outcome of each review/meeting, the SMC will make a recommendation as to the advisability of proceeding with study vaccinations (as applicable), and to continue, modify, or terminate this study.

11.1.2 Monitoring of the Study

The clinical monitor, as a representative of the sponsor, has the obligation to follow the study closely. In doing so, the clinical monitor will visit the investigator and study site at periodic intervals (including remote monitoring activities), in addition to maintaining necessary telephone and letter contact. The clinical monitor will maintain current personal knowledge of the study through observation, review of study records and source documentation, and discussion of the conduct of the study with the investigator and personnel.

All aspects of the study will be carefully monitored, by the sponsor or its designee, for compliance with applicable government regulation with respect to current GCP and current standard operating procedures.

11.1.3 Inspection of Records

Investigators and institutions involved in the study will permit study-related monitoring, audits, IEC review, and regulatory inspections by providing direct access to all study records. In the event of an audit, the investigator agrees to allow the sponsor, representatives of the sponsor, or a regulatory agency access to all study records.

The investigator should promptly notify the sponsor and the CRO of any audits scheduled by any regulatory authorities and promptly forward copies of any audit reports received to the sponsor.

11.2 Management of Protocol Amendments and Deviations

11.2.1 Modification of the Protocol

Any changes in the required procedures defined in this protocol, except those necessary to remove an apparent, immediate hazard to the subject, must be reviewed and approved by the sponsor or its designee. Amendments to the protocol must be approved by the IEC before subjects can be enrolled into an amended protocol. Letters of amendment or clarification do not need to be approved by the IEC.

11.2.2 Protocol Deviations

A deviation from the protocol is an unintended or unanticipated departure from the procedures or processes approved by the sponsor and the IEC and agreed to by the

investigator. A significant deviation occurs when there is nonadherence to the protocol or to local regulations or ICH GCP guidelines that may or may not result in a significant, additional risk to the participant or impacts the integrity of study data. Deviations will be assessed with Sponsor involvement and deemed significant (major) or of minor significance prior to database lock.

The investigator or designee must document and explain in the participant's source documentation any deviation from the approved protocol. The investigator may implement a deviation from, or a change of, the protocol to eliminate an immediate hazard/safety risk to study participants without prior IEC approval. As soon as possible after such an occurrence, the implemented deviation or change, the reasons for it, and any proposed protocol amendments should be submitted to the IEC for review and approval, to the sponsor for agreement, and to the regulatory authorities, where required.

In order to keep deviations from the protocol to a minimum, the investigator and relevant site personnel will be trained in all aspects of study conduct by the sponsor/sponsor representative. This training will occur either as part of the investigator meeting or site initiation. Ongoing training may also be performed throughout the study during routine site monitoring activities.

11.3 Study Termination

Although the sponsor has every intention of completing the study, the sponsor reserves the right to discontinue the study at any time for clinical or administrative reasons.

The end of the study is defined as the date on which the last subject completes the last visit (includes follow-up telephone call for long-term safety).

13.1 Appendix: Schedule of Events

Table 13-1 **Schedule of Events**

Subject Population	Screening		Treatment Period							EOS	
	All Subjects	All Subjects	Safety Lead-In Subjects ONLY	All Subjects	Subjects NOT in Substudy	Subjects Participating in Substudy ONLY ^d			All Subjects		
Study Visit	Screening	V1	S1 ^b	V2	V3 ^c	SSV3	SSV4	SSV5	SSV6	Unscheduled ^e	EOS/Early Termination
Study Day	-30 to 1 ^a	1	8	29	85	85	92	99	113	-	169
Window allowance	30	0	+3	+7	+14	+20	+3	+2	+7	-	+30
Informed consent	X					X ^{f,g}					
Inclusion/exclusion criteria	X	X ^{f,g}				X ^{f,g}					
Demographic and baseline data ^h	X										
Medical history ⁱ	X	X ^{f,g}									
Concomitant medication ^j	X	X ^g	X	X	X ^k	X ^g	X	X	X	X ^k	X ^k
Concomitant vaccines ^l	X	X ^g	X	X	X	X ^g	X	X	X	X	X
Targeted physical examination ^m	X	X ^g	X	X	X	X ^g	X	X	X	X	X
Vital sign measurements ⁿ	X	X ^g				X ^g				X	
Urine pregnancy test ^o	X	X ^g				X ^g				X	
SARS-CoV-2 test for active infection (within 72 hrs prior to vaccination) ^p		X				X					
Study vaccination ^q		X				X					
Immediate reactogenicity		X ^r				X ^r					
Subject diary dispensed ^s		X				X					

Subject Population	Screening		Treatment Period								EOS
	All Subjects	All Subjects	Safety Lead-In Subjects ONLY	All Subjects	Subjects NOT in Substudy	Subjects Participating in Substudy ONLY ^d				All Subjects	
Study Visit	Screening	V1	S1 ^b	V2	V3 ^c	SSV3	SSV4	SSV5	SSV6	Unscheduled ^e	EOS/Early Termination
Study Day	-30 to 1 ^a	1	8	29	85	85	92	99	113	-	169
Window allowance	30	0	+3	+7	+14	+20	+3	+2	+7	-	+30
Subject diary reviewed ^f			X	X			X			X	
Nasal sampling for immunogenicity laboratory tests		X ^g		X	X	X ^g			X		X
Mid-turbinete/nasopharyngeal sampling for B. pertussis culture or PCR			X	X ^u	X ^u		X	X			
Blood sampling for immunogenicity laboratory tests		X ^g		X	X	X			X		X
Blood sampling for cellular-mediated Th1 and Th2 responses		X ^b	X			X ^v			X ^v		
Any TEAE (following most recent vaccination)		X	X	X		X	X	X	X	X	
Any MAAEW, AESI, or SAE (following first vaccination)		X	X	X	X	X	X	X	X	X	X
EOS form											X

^a Screening visit may occur on Day 1 prior to study vaccination.

- ^b Safety lead-in subjects (only) to complete procedures listed under Study Visit S1; PBMCs to be collected in a subset of subjects.
- ^c Subjects not participating in the substudy are to complete procedures listed under Study Visit V3 for Day 85. Subjects in the safety lead-in cohort who are not participating in the substudy are not required to provide samples on Day 85 and may complete this visit remotely.
- ^d Subjects participating in the substudy (only) to complete procedures listed under Study Visits SSV3, SSV4, SSV5, and SSV6.
- ^e Procedures listed for an Unscheduled study visit are optional and dependent on the cause for the visit itself. An unscheduled study visit may occur at any time between enrolment and Day 169/EOS.
- ^f Reviewed and/or updated.
- ^g Performed prior to vaccination.
- ^h Such as date of birth (where allowed by local regulations), sex, race, ethnicity, weight, and height (with derived BMI and Z-score).
- ⁱ Including prior and ongoing chronic medical conditions and past surgeries.
- ^j Concomitant medications will include all medications and OTC products (including herbal supplements and multivitamins) taken by the subject from the time of signing the ICF through Day 29 (and from Day 85 [following study vaccination] through Day 113 for subjects participating in the optional substudy), or through an early termination visit, if prior to these time points. The use of anti-pyrogenic medication will be specifically queried by diary during the 7 days following any study vaccination.
- ^k Only concomitant medications associated with any MAAE (through 84 days following any study vaccination); or AESI or SAE (through Day 169/EOS) will be recorded.
- ^l Vaccines received outside of the study will be specifically queried during each visit and recorded through Day 169/EOS.
- ^m Targeted physical examination at screening and Day 1 (prior to vaccination) to include head and neck (inclusive of nasal cavity and oropharynx), respiratory, cardiac, abdomen, and lymph nodes associated with the upper extremity, head, and neck. Targeted physical examination at all other times will be symptom-directed and performed at the discretion of the investigator. Height and weight will be measured at screening only.
- ⁿ Vital sign measurements (heart rate, body temperature) will be collected once before vaccination and then at 30 (+30) minutes after the last study vaccination (i.e., after IM vaccination on Day 1). For the safety lead-in cohort, a minimum of 30 minutes must occur between intranasal and IM vaccinations on Day 1, and medical assessment will occur prior to the second vaccination to allow for advancement. Temperature (oral or tympanic) will also be recorded daily in a subject diary for 7 consecutive days starting the day following any study vaccination (retrospective of the highest value in the previous 24 hours).
- ^o Female subjects of childbearing potential only who have become heterosexually active. To be performed at the discretion of the investigator based on history taking.
- ^p SARS-CoV-2 testing should be performed within approved national guidelines with tests that are approved through a (minimum) of emergency use authorization. Minimally invasive testing should be considered for the comfort of subjects. Subjects need to have accepted negative test results within 72 hours prior to vaccination. Repeat testing is allowed on multiple occasions. For the substudy, subjects are not considered to have a protocol violation if a retest for SARS-CoV-2 exceeds the study window.

- ^q On Day 1, intranasal vaccination will occur prior to IM vaccination with a minimum of 10 minutes (minimum of 30 minutes for subjects in the safety lead-in cohort of 11 to 17 year olds) between intranasal and IM vaccinations.
- ^r Immediate reactogenicity will be assessed at 30 minutes (+30 minutes) after the last study vaccination of the Day (i.e., after IM vaccination on Day 1, after nasal vaccination on Day 85), prior to release from clinical observation.
- ^s All subjects will record maximum daily reactogenicity in a subject diary for 7 consecutive days starting the day following any study vaccination (retrospective of the highest value in the previous 24 hours). Subjects will be instructed that should they have reactogenicity with a potential toxicity grade 3 at any time, they should contact the site on the same day and be seen or referred to a qualified medical facility within 24 hours.
- ^t Trained clinical staff will review the information from the subject diaries with the subjects and apply a standard toxicity grade (refer to Section 13.2) to any reactogenicity event. The diary will be reviewed following the first visit after vaccination for all subjects.
- ^u Subjects not in the safety lead-in cohort will be randomly assigned (1:1) to provide mid-turbinate/nasopharyngeal samples on either Day 29 or Day 85; however, if a subject cannot provide a sample on Day 29 (for any reason), the subject should provide a sample on Day 85 (this will not be considered a protocol deviation).
- ^v Collection of an extra 20 mL of blood for cellular-mediated immunity may be an option in a select number of individuals who are in the substudy (up to 45 subjects). This will not involve extra venipuncture, but only collection of additional volume.
- ^w Medically attended AEs will be monitored through 84 days following any study vaccination.

13.2 Appendix: Toxicity Grading Scales

Table 13-2 Local Reactogenicity Grading Scale

Variable	Grade 1	Grade 2	Grade 3
Pain/tenderness ^a	Easily tolerated, causes no or minimal limitation of use of limb	Sufficiently discomforting, interferes with greater than minimal limitation of use of limb	Causing inability to perform usual social and functional activities
Redness ^{b,c}	Evidence of redness that is ≤ 2.5 cm in diameter	>2.5 cm in diameter with $<50\%$ of upper extremity surface area segment involved	$\geq 50\%$ upper extremity surface area segment involved OR ulceration OR infection OR phlebitis OR sterile abscess OR drainage
Swelling ^{b,c}	Evidence of swelling that is ≤ 2.5 cm in diameter	>2.5 cm in diameter with $<50\%$ of upper extremity surface area segment involved	$\geq 50\%$ upper extremity surface area segment involved OR ulceration OR infection OR phlebitis OR sterile abscess OR drainage

Note: Local reactogenicity to be evaluated after an IM injection only. Grade 0 will be the classification if the observation is less than a grade 1. Any grade 3 reactogenicity event that leads to an unscheduled visit to a healthcare provider will be recorded as an MAAE.

^a To be graded by investigator based on subject diary.

^b Grade to be applied by data management based on measurement recording unless grade 3 is noted with other characteristics by the investigator.

^c If redness or swelling exceeds 100 mm or $>50\%$ of upper extremity surface area, or involves the shoulder, elbow, or chest, or prevents everyday activity, then subjects must be evaluated and a swelling assessment eCRF will be completed.

Source: Adapted from DAIDS Version 2.1, 2017.

Table 13-3 Nasal/Respiratory Reactogenicity Grading Scale

Variable	Grade 1	Grade 2	Grade 3
Runny nose/nasal congestion	Noticeable but does not interfere with normal everyday activity (eg, aware but not troubled, rarely wipes/blows nose, breathing through nose noted)	Moderate discomfort that interferes with normal everyday activity, troublesome (eg, wipe/blow nose occasionally, noisy nose breathing, occasional mouth breathing, “nasally” speech)	Significant discomfort, prevents normal everyday activity, and/or seeks medical care (eg, wipe/blow nose frequently, mouth breathing most of the time due to congestion, consistent “nasally” speech)
Sore/irritated throat (‘scratchy’)	Noticeable but does not interfere with eating or drinking (eg, aware but not troubled)	Moderate discomfort that interferes with eating or drinking, troublesome, affects oral intake	Significant discomfort, prevents eating or drinking, and/or seeks medical care; troublesome to the level of preventing oral intake
Cough	Noticeable but does not interfere with normal everyday activity or sleeping (eg, aware but not troubled, a few short episodes)	Frequent cough that interrupts normal everyday activity or sleeping, troublesome (eg, coughing but only rare episodes of prolonged coughing)	Significant and repetitive coughing that prevents everyday activity or sleep, or seeks medical care (eg, frequent coughing, occasional episodes of prolonged coughing)
Sneezing	Noticeable but does not interfere with normal everyday activity (eg, aware but not troubled, a few short episodes)	Moderate discomfort that interferes with normal everyday activity, troublesome (eg, occasional bouts of sneezing)	Significant discomfort, prevents everyday activity, and/or seeks medical care (eg, frequent/repeated sneezing episodes)
Nasal or sinus pain/irritation	Noticeable but does not interfere with normal everyday activity (eg, aware but not troubled, noted discomfort)	Moderate discomfort that interferes with normal everyday activity, troublesome (facial pain/pressure)	Significant discomfort, prevents everyday activity, and/or seeks medical care; or induces nosebleed ^a
Difficulty breathing/wheezing	Audible wheeze (whistling sound) occasionally noted with exhale or inhale but does not interfere with normal everyday activity	Audible wheeze and/or shortness of breath with activity (eg, nasal flaring, chest tightness, rapid breathing at rest/minimal activity), interferes with normal everyday activity	Requires bronchodilator use or accompanied by respiratory distress or hypoxemia

Note: Grade 0 will be the classification if the observation is less than a grade 1. Any grade 3 reactogenicity event that leads to an unscheduled visit to a healthcare provider will be recorded as an MAAE.

^a Epistaxis (nosebleed) should be entered as an AE and graded accordingly.

Source: Adapted for age and aligned with FluMist Monograph.

Table 13-4 Systemic Reactogenicity Grading Scale

Variable	Grade 1	Grade 2	Grade 3
Fever ^a	38.0 – 38.4 °C (100.4°F – 101.1°F)	38.5 – 38.9 °C (101.2°F – 102.0°F)	39.0 – 40.0 °C (102.1°F – 104.0°F)
Headache	Easily tolerated, causing no or minimal interference with daily activities	Causing greater than minimal interference with usual social and functional activities Interferes with normal everyday activity	Prevents performance of normal social and functional activities
Fatigue/malaise (decreased activity)	Easily tolerated	Interferes with normal everyday activity	Prevents normal everyday activity
Loss of appetite/anorexia	loss of appetite but no decrease in oral intake	Decreased oral intake but no weight loss	Decreased oral intake with weight loss or evidence of dehydration
Vomiting	Transient or intermittent AND no or minimal interference with oral intake	Frequent episodes with no or mild dehydration	Persistent vomiting resulting in need of aggressive rehydration (eg IV hydration)
Diarrhoea	Transient or intermittent episodes of unformed stools OR increase of ≤ 3 stools over normal in a 24-hr period	Persistent episodes of unformed or watery stools OR increase of 4-6 stools over normal in a 24-hr period	Increase of >7 stools a 24-hr period OR IV fluid replacement indicated
Nausea	Transient or intermittent AND no or minimal interference with oral intake	Persistent nausea with decrease in oral intake for 24 hrs	Persistent nausea with need for fluid replacement (eg, IV hydration)
Myalgia (muscle aches)	Muscle pain beyond the site of injection causing no or minimal interference with usual social and functional activities	Muscle pain beyond the site of injection causing greater than minimal interference with usual social and functional activities	Muscle pain causing inability to perform usual social and functional activities
Acute allergic reaction/urticaria	Localized without medical intervention	Localized with medical intervention OR mild angioedema without intervention	Generalized OR angioedema with intervention

Note: Grade 0 will be the classification if the observation is less than a Grade 1. Any grade 3 reactogenicity event that leads to an unscheduled visit to a healthcare provider will be recorded as an MAAE.

^a Temperature may be oral, tympanic, or noncontact (clinic only). Temperature greater than 40.0 °C (104.0 °F) is considered an SAE and subjects should seek medical attention immediately.

Source: Adapted from DAIDS Version 2.1, 2017.

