4.1.2 Exclusion Criteria

Subjects meeting any of the following criteria (by review of medical history and subject intake) will be excluded from the study:

1. The subject has a history of pertussis-containing vaccination (inclusive of school vaccination programs) or documented *B. pertussis* infection within 3 years prior to Day 1 and/or a history of Td-containing vaccination (without pertussis vaccine component) within 1 month prior to Day 1.

2. The subject has a chronic significant illness actively being treated or a history of recent intervention for worsening or fluctuating symptoms (at the discretion of the investigator).
3. The subject has a history of cancer (malignancy).
4. The subject has a congenital, hereditary, or acquired disease or disorder classified as autoimmune, immunodeficient, coagulopathy, hepatic, renal, neurologic (including a history of Bell's palsy), or moderate to severe cognitive. (Attention deficit hyperactivity disorder permitted.)
5. The subject currently uses smoking products (including vaping and e-cigarettes) and is unwilling to refrain from use from Day 1 through Day 29 following any study vaccination.
6. The subject has received immunoglobulin, blood-derived products, systemic corticosteroids (at a dose of >10 mg per day for more than 10 days), or other immunosuppressant drugs within 90 days prior to Day 1.
7. The subject has any chronic pulmonary disease requiring active medication or pulmonary therapies, with the following exceptions:
 - a) Subjects with exercise-induced bronchospasm, if currently well controlled, who are willing to refrain from intense exercise for 7 days following study vaccination or
 - b) Subjects with Step 1 (intermittent) asthma classification who have not had an exacerbation requiring oral systemic corticosteroids in the past year; have an FEV1 documented to be >80%; do not have restrictions in normal activity due to breathing issues; and have used a short-acting beta-agonist less than or equal to 2 days per week over the past 2 months.

NOTE: Subjects in the safety lead-in cohort are not allowed to have these exceptions.

8. The subject has a history of oro/nasopharynx surgery (eg, adenoidectomy, tonsillectomy) within 60 days prior to Day 1.
9. The subject has a known hypersensitivity to latex or any component of any study vaccine. Specific to Boostrix: the subject has known hypersensitivity to neomycin or

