6.3.5.3 Reporting Adverse Events

Adverse events reported or observed during the study will be recorded on the AE page in the eCRF.

An AE is any unfavourable and unintended sign, symptom, or disease. The occurrence of an AE may come to the attention of study personnel during study visits and interviews of a study recipient presenting for medical care, or upon review by a study monitor. A single AE may have a constellation of signs/symptoms and the single most precise Medical Dictionary for Regulatory Activities (MedDRA) term should be utilized as the AE classification to avoid duplication of AEs.

Adverse events will be captured on the appropriate data collection form and eCRF. Information to be collected for unsolicited nonserious AEs includes event description, date of onset, licensed study physician's assessment of severity and relationship to study vaccination and alternate aetiology (if not related to study vaccination), date of resolution of the event, seriousness, and outcome. Adverse events occurring during the collection and reporting period will be documented appropriately regardless of relationship (as defined in Section 6.3.5.7).

Any medical condition that is present at the time that the subject is screened will be considered as baseline (recorded as medical history) and not reported as an AE; however, if the severity of any pre-existing medical condition increases, it will be recorded as an AE.

Adverse events must be graded for severity and assessed for relationship to study vaccination. Adverse events characterized as intermittent require documentation of onset and duration of each episode. The start and stop date of each reported AE will be recorded on the appropriate data collection form and eCRF.

Adverse events resulting from concurrent illnesses, reactions to concurrent illnesses, reactions to concurrent medications, or progression of disease states must also be reported. All AEs will be followed to adequate resolution. The MedDRA will be used to code all AEs.

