6.5 Vaccination Pause Rules

Further enrolment and study vaccinations will be halted (paused) for SMC review/recommendation if any of the following are reported:

- Any subject experiences ulceration, abscess, or necrosis in the nose that is considered related to study vaccination, through 28 days following study vaccination.
- Any subject experiences severe respiratory symptoms of laryngospasm, shortness of breath or wheezing (grade 3 or greater) within 3 days of study vaccination.
- Any subject experiences an SAE considered related to study vaccination from the time of the vaccination through the subject's last study visit.
- More than 12 subjects report a grade 3 fever within 7 days of study vaccination that is attributed to study vaccination when no other cause can be found (corresponding to an incidence rate of approximately 3% for Boostrix).

Grading scales for solicited reactogenicity events are included in Section 13.2.

If any of the vaccination pause rules are met following any subject receipt of study vaccination, then this study will not continue with the remaining enrolments or future study vaccinations without a review by the SMC and a recommendation from the SMC to proceed (with or without alteration of protocol). Vaccination windows will be adjusted for any such pause to allow subjects to remain within the expected schedule of events. All events that classify for vaccination pause rules will be entered as AEs.

The sponsor retains the authority to suspend additional enrolment and study interventions or administration of study vaccine during the entire study, as applicable.

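### Wheeze needing an inhaler is always grade 3, yet exclusion 7b admits children who use one, so habitual treated wheeze can enter the by-grade tables and pause the trial

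*Protocol*

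**What the plan says.** **Eligibility (Protocol 4.1.2, exclusion 7).** Chronic lung disease needing active treatment is excluded, with two exceptions. 7a covers well-controlled exercise-induced bronchospasm, provided the child will avoid intense exercise for 7 days after vaccination. 7b covers "Subjects with Step 1 (intermittent) asthma classification who have not had an exacerbation requiring oral systemic corticosteroids in the past year", whose FEV1 and normal activity are adequate, and who "have used a short-acting beta-agonist less than or equal to 2 days per week over the past 2 months". A note adds that "Subjects in the safety lead-in cohort are not allowed to have these exceptions".

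**Grading (Protocol 13.2, Table 13-3; SAP 9.1, Table 9-1-2).** For difficulty breathing/wheezing, grades 1 and 2 turn on interference with everyday activity. Grade 3 reads "Requires bronchodilator use or accompanied by respiratory distress or hypoxemia". The wording is the same in both documents, and neither adds a comparison with the child's usual state.

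**Pause rule (Protocol 6.5).** "Further enrolment and study vaccinations will be halted (paused) for SMC" review if any listed event is reported. The second bullet is: "Any subject experiences severe respiratory symptoms of laryngospasm, shortness of breath or wheezing (grade 3 or greater) within 3 days of study vaccination". The other three bullets each carry a causal condition, for example "Any subject experiences an SAE considered related to study vaccination".

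**Baseline conditions (Protocol 6.3.5.3).** "Any medical condition that is present at the time that the subject is screened will be considered as baseline" and is not reported as an AE unless its severity increases.

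**The concern.** The eligibility criteria knowingly admit children who sometimes wheeze and use a reliever inhaler. In the grading row, needing a bronchodilator is sufficient for grade 3 on its own, since the alternatives are joined by an or. A 7b child must have no activity restriction from breathing problems, so that child's ordinary wheeze fits grade 1 until the usual inhaler is needed, when it becomes grade 3. One such event within 3 days meets the second pause bullet.

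Two things are at stake. First, the by-grade reactogenicity tables would mix new bronchospasm with ordinary asthma management, and grade 3 breathing difficulty is a result that readers of a live intranasal vaccine trial will look at closely. Second, enrolment and vaccination could stop for an event that the eligibility criteria make foreseeable. The lead-in review cannot show how often this happens, because the 45 lead-in subjects may not enter under the exceptions.

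**Working it through.** **Text check**

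1. Does the grade depend on the usual state? No. Neither table has a baseline clause, and neither refers to Protocol 6.3.5.3.
2. Does the pause rule allow for another cause? Not in the second bullet. The nasal ulceration and SAE bullets require relatedness. The fever bullet requires attribution to vaccination with no other cause found.
3. Does 6.3.5.3 settle the matter? Not clearly. It keeps unchanged pre-existing conditions out of AE reporting, while 6.5 says every event meeting a pause rule is entered as an AE. For unchanged asthma that reaches grade 3 through inhaler use, the two sections point in different directions.
4. Which endpoint is affected? The primary safety endpoint (Protocol 2.1, 7.4.1.2; SAP 9.1) counts subjects with solicited events, so a wheezing child counts once at grade 1 or grade 3. Incidence by grade and maximum severity are secondary endpoints (Protocol 2.2, 7.4.3.3). Those are where the grade matters.
5. The pause bullet also allows for a grade above 3, on a scale that ends at 3.

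**Illustration of size**

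The documents give no rate for this event, so there is no planned figure to reproduce.

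Inputs from the documents:
- about 360 subjects, of whom the first 45 are the lead-in: 360 − 45 = 315 can enter under the exceptions
- a ceiling of 2 use-days a week
- a 3-day pause window
- a 7-day diary

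Assumptions:
- m children enter under 7b
- each uses an inhaler on u days a week, independently from day to day
- a fraction w of use-days is for wheeze rather than prevention

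Per child over 3 days, p = 1 − (1 − w·u/7)³. Across children, P(at least one trigger) = 1 − (1 − p)^m.

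Example: u = 0.25 and w = 1 give p = 1 − (1 − 0.25/7)³ = 0.103. With m = 5, P = 1 − (1 − 0.103)⁵ = 0.42.

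| u (days/week) | w | p over 3 days | P, m = 3 | P, m = 5 |
|---|---|---|---|---|
| 0.25 | 0.5 | 5.3% | 15% | 24% |
| 0.25 | 1 | 10.3% | 28% | 42% |
| 0.5 | 1 | 19.9% | 49% | 67% |
| 1 | 1 | 37.0% | 75% | 90% |
| 2 | 1 | 63.6% | 95% | 99% |

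Five children are 5/315 = 1.6% of those who can enter under the exceptions; three are about 1%.

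For the by-grade tables, replace the exponent 3 with 7. At u = 0.25, about 12% of such children (w = 0.5) or 22.5% (w = 1) would have a background grade 3 event. At u = 2 and w = 1 it is 90.5%. With five children, the expected number is about 0.6, 1.1 and 4.5, spread over three arms.

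These figures cover the first dose only. They ignore the temporary hold in Protocol 4.1.3, which would lower them somewhat. They also ignore the second BPZE1 dose given to up to 120 substudy subjects (Protocol 3.1.1), which opens another 3-day window.

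**The case against.** Much of the opposing case stands, and it limits the point.

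- **Any inhaler use counts.** A reader might infer that every puff is grade 3. The row grades breathing difficulty or wheeze that needs a bronchodilator, so preventive or symptom-free use is outside it.
- **The primary safety endpoint is inflated.** A reader might infer this because the objective mentions toxicity scoring. The endpoint and its analysis count occurrence, so the grade does not alter it.
- **The treatment comparison is biased.** Allocation is 1:1:1 and one arm receives nasal placebo, so background use should balance on average. The effect is extra grade 3 counts in all arms.
- **Existing safeguards.** 7a subjects agree to avoid intense exercise throughout the diary period, which limits their usual trigger. Protocol 4.1.3 allows vaccination to be deferred for recent acute respiratory symptoms. Both reduce the frequency, but neither deals with habitual wheeze after vaccination in a 7b child.
- **The provisions contradict each other outright.** That is too strong, since they can all be followed at once. The bullet also speaks of severe symptoms, which leaves some room for judgement, although its parenthesis ties severity to grade. Sections 6.3.5.3 and 6.5 read together might support not treating unchanged asthma as a pause event, but neither says so.
- **The pause rule is deliberate caution.** This is the first study of BPZE1 in school-age children, and a pause means SMC review, not termination. A trigger without a causality condition is defensible. The plan should then show that it was chosen with the 7b children in mind.

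**Conclusion.** The point holds in limited form. Habitual wheeze treated with the usual inhaler in a child admitted under 7b can be counted as grade 3 in the secondary by-grade tables in any arm, and one such event within 3 days meets a pause rule that has no causality condition. On days 4 to 7 it is a grade 3 count without a pause.

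The size is uncertain because the documents give only the 2-days-a-week ceiling, with no number of such children and no typical use. With five children, the chance of at least one trigger after dose 1 runs from about 24% to 99% over the range shown. The top figure assumes that every child is at the ceiling and that all use is for wheeze, so it should not be read as a forecast. Even the lowest case tabulated, three children with infrequent use and half of it for wheeze, gives 15%.

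The documents do not show that the primary safety result is affected, that the arms are compared unfairly, or that the pause rule itself is wrong.

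**What to change.** 1. Keep the raw Table 13-3 grade as recorded.
2. Record each subject's usual wheeze and bronchodilator frequency at Day 1. Screening for 7b already has to establish reliever use over the previous 2 months.
3. In the SAP, tabulate grade 3 difficulty breathing/wheezing separately for subjects admitted under 7a or 7b and for all others, by arm.
4. The sponsor and SMC should reconcile exclusion 7, Table 13-3 / SAP Table 9-1-2, Protocol 6.3.5.3 and the second pause bullet in 6.5. They should state how that bullet applies to children admitted under the exceptions, and define or remove its reference to grades above 3. Which clinical rule applies is for them to decide.

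The cost is about one eCRF field, one extra split of a safety table, and the clarifying text.
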